In academic centers, lacerations are often repaired by residents. Approximately 60% of obstetrics/gynecology (ob/gyn) residents in residency programs in the United States admitted to not having any didactic teaching on episiotomy repair and no formal teaching on pelvic floor anatomy and when engaged in the repair, were supervised only a third of the time [5]. It has been shown that with the rise in cesarean sections and decline in operative vaginal deliveries, the prevalence of third- and fourth-degree lacerations has been decreasing in recent years and this has resulted in limited exposure to repairs and lack of residents' confidence to properly repair advanced perineal lacerations [6,7]. One study evaluating 40 ob/gyn residents at 13 different residency programs showed an overall pass rate of only 42.5% with many residents missing critical steps of the repair [7].

Surgical models have been increasing in popularity and have been shown to improve surgical skills and knowledge base [3, 6]. It has further been shown that anatomical models and hands-on workshops on how to repair fourth-degree lacerations can improve knowledge and surgical technique [3]. Beef tongue models have been used in the education and assessment of surgical skills for fourth-degree laceration repair [3,6,8]. One study compared a beef tongue

model to sponge model showing all participants preferred the beef tongue model [6]. Siddiqui et al used a beef tongue model to validate a task specific Objective Structured Assessment of Technical Skills (OSATS) for the repair of fourth-degree obstetric lacerations [9]. We recently demonstrated a modified beef tongue model that used beef tripe (small intestine) for the anal mucosa and chicken leg segments for the anal sphincter muscle analogs to create a realistic model [10].

Given the decreasing number of third- and fourth degree lacerations and poor resident confidence and performance demonstrated in these repairs, better and more widely used teaching methods are necessary. The modified beef tongue model serves as a realistic tool to teach and assess fourth-degree laceration anatomy and repair. While workshops have been shown to improve knowledge and technical skills [3], these require significant time, expense, and organization. Instructional videos can be used to serve the same purpose without these limitations and thus could lead to wider use as a didactic intervention for fourth-degree repair. Instructional videos have been evaluated for fourth-degree repair in a limited manner. One study showed an improvement in knowledge after an instructional video but only in residents with no prior experience in repair of lacerations [8] and we could not find any that assess change in outcomes on technical surgical skills.

We believe that an instructional video that utilizes the modified beef tongue model is a valuable educational tool to increase resident knowledge, confidence, and surgical ability to properly repair a fourth degree laceration. The aim of this study is to compare technical skills outcomes with an instructional video using the modified beef tongue model to a modified beef tongue hands-on educational workshop. Our hypothesis is that participants will have similar

improvements in their technical skills for repair of fourth-degree laceration as evaluated by an objective structured assessment of technical skills (OSATS).

Null hypothesis: Participants undergoing the modified beef tongue instructional video will have worse outcomes on an objective structured assessment of technical skills (OSATS) for repair of fourth degree obstetric laceration than those undergoing a modified beef tongue educational workshop.

Significance

There are no studies evaluating the use of an instructional video for fourth-degree laceration repair to assess change in outcomes on technical skills.

Study Design

Inclusion Criteria

PGY1-4 residents in an obstetrics and gynecology training program

Exclusion Criteria

None

Intervention

Instructional video using the modified beef tongue model or instructional workshop using the modified beef tongue model.

Primary outcome

The primary outcome will be change in technical skills score measured as change from baseline in a validated objective structured assessment of technical skills (OSATS) for repair of fourth degree obstetric laceration.

Secondary outcomes

1. Participant preference of model between instructional video and instructional workshop
2. Knowledge assessed by written test performed pre- and post-intervention
3. Participant's confidence in fourth-degree laceration repair as measured by change in confidence score from pre- to post-intervention.
4. Time taken for repair of fourth degree laceration
5. Ease of use of the model as reported by participants
6. Overall satisfaction of the model
7. Model realism
8. Factors associated with higher knowledge scores (e.g. PGY level, number of prior repairs, prior didactics)

Protocol in detail

Institutional Review Board approval and written informed consent will be obtained prior to initiation of the study. All obstetrics and gynecology residents at the University of Alabama will be eligible for the study.

Eligible residents who desire will be enrolled and consented for the trial. Participants will then complete a short pre-intervention knowledge assessment written test and be asked to rate their confidence level in completing a fourth-degree repair based on a Likert scale. The written test is the same as the one used by Patel et al to evaluate residents' knowledge about

fourth-degree laceration repair [8]. The questions are based on Williams's obstetric chapter on episiotomy repair [11] and showed construct validity given a significant difference in scores between postgraduate year (PGY)-1 and PGY-4 residents [8]. Participants will also complete a baseline objective structured assessment of technical skills (OSATS) assessment for repair of fourth-degree obstetric laceration on a commercial anatomical replica, the Sultan Anal Sphincter Trainer (Limbs & Things Inc, Savannah, Georgia). This model comes with a replaceable perineal pad that allows approximately 24 repairs before replacement is necessary. The validated OSATS used will be the assessment described by Siddiqui et al and validated on a surgical model [9]. The repair will be videotaped and then distributed to evaluators who will use the 20 item task specific checklist described by Siddiqui et al [9]. The time taken for the repair will be recorded.

Demographic and baseline data will be collected on the participants including PGY level, number of fourth-degree lacerations performed, whether they have read a textbook regarding fourth-degree laceration repair, whether they have read a journal article regarding fourth-degree laceration repair, whether they have attended a didactic session in pelvic anatomy, and whether they have attended a didactic session on fourth-degree laceration repair.

Participants will then be randomized into two groups. Randomization will be performed using a computer-generated block design so that each group has a balanced number of residents in each postgraduate year training level. One group will be randomized to the modified beef tongue video and one will be randomized to the modified beef tongue instructional workshop. The modified beef tongue video group will be given an instructional video created using the modified beef tongue model to show anatomy and proper repair of the laceration. The group randomized to the modified beef tongue instructional workshop will undergo an interactive

workshop using the modified beef tongue model to show anatomy and proper repair of the laceration.

The modified beef tongue for the video and workshop will be prepared according to the model previously described in the literature [11]. The modified model includes beef tripe (small intestine) used for anal mucosa and chicken leg muscles for anal sphincter muscle analogs. The tripe is tunneled through the body of the trimmed beef tongue and sutured like an ostomy to simulate the anal canal. The tongue is incised toward the tripe “anal canal.” Chicken leg muscles are tunneled from the incision out to the cut edges of the beef tongue to create anal sphincter muscle analogs.

Following the didactic intervention, participants from each group will be given the written knowledge assessment test again and the objective structured assessment of technical skills (OSATS) for repair of fourth-degree laceration on the commercial anatomical replica again. The time taken for the repair will be recorded. Residents will also be asked to evaluate model realism, ease of use, and satisfaction using a Likert scale. The residents will be asked to assess their confidence again using a Likert scale.

The participants will then be crossed over and those who were initially randomized to the video group will then undergo the instructional workshop and the ones initially in the workshop group will be given the instructional video. Participants will then be asked to rate their overall preference between models on a scale of 1 to 10 with 1 being the video and 10 being the instructional workshop. They will also complete the written knowledge test again.

The results of this trial may help to inform to a cost- and time-efficient manner of instruction on the repair of 3rd and 4th degree lacerations. A weakness is that it is unclear whether this will translate to effectiveness at the time of an actual third- and fourth-degree repair.

Statistical Analysis Plan

Given the fixed set of residents, a post hoc power analysis will be performed. Categorical variables will be analyzed using chi-squared or Fisher exact tests and continuous variables will be analyzed using student t-tests. The mean scores of knowledge assessment and from the Objective Structured Assessment of Technical Skills (OSATS) as well as the change in scores pre- and post-intervention will be compared using Student t-tests. Differences in improvement scores between the two groups will be further examined using linear regression models, adjusting for baseline score and year of training. Differences in the score improvement between the two study groups and for each resident year will be analyzed using Wilcoxon rank test.

References

1. Vale de Castro Monteiro M, Pereira GM, Aguiar RA, Azevedo RL, Correia-Junior MD, Reis ZS. Risk factors for severe obstetric perineal lacerations. *Int Urogynecol J* 2016;27:61–7.

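### The hypothesis is that video and workshop give similar OSATS gains, but the SAP tests only for a difference, with no margin, so no planned result can support it

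*Combined protocol and SAP*

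**What the plan says.** The hypothesis and the null stand in the introductory text just before the Significance heading. The hypothesis reads "Our hypothesis is that participants will have similar" improvement in technical skills. The null is that "Participants undergoing the modified beef tongue instructional video will have worse outcomes on an objective structured assessment of technical skills (OSATS") than those attending the workshop; it does not say how much worse. The aim in the same section is neutral: to compare the two methods on technical skills.

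Under Primary outcome, "The primary outcome will be change in technical skills score measured as change from baseline" on the OSATS. The instrument is a "20 item task specific checklist"; no SD or expected gain is given.

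The Statistical Analysis Plan lists three analyses that bear on this outcome:

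- a t-test comparing the arms on mean scores and on the gain from before to after teaching;
- an adjusted model, described thus: "Differences in improvement scores between the two groups will be further examined using linear regression models, adjusting for baseline score and year of training";
- a rank test (Wilcoxon) on the gain, by arm and within each PGY level.

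On sample size it says only: "Given the fixed set of residents, a post hoc power analysis will be performed". No section states a margin, an alpha level, a sidedness, a confidence level, a confidence-limit rule or a definition of similar. The SAP paragraph shows no sign of redaction.

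**The concern.** Rejecting a null of *video worse* means concluding *video not worse*. To do that for a video that is about as good as the workshop, the plan needs a margin and a rule saying which confidence limit must clear it. The SAP has neither. Its analyses address whether the difference is zero, and failing to reject a zero difference is not evidence that the difference is small.

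The trial's rationale is that a video could replace a workshop that costs more time and organization, so the conclusion readers will look for is that the video is no worse. If p>0.05 is taken as that conclusion, a less precise study is more likely to reach it. The documents do not say that a non-significant result will be read this way, but no rule prevents it. The post hoc power calculation does not help: it sets no margin and cannot turn non-significance into evidence of similarity.

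**Working it through.** The plan states no sample size, power, alpha or margin, so there is no figure of its own to reproduce. What follows is illustration.

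**Assumptions, none from the documents.** Equal arms of n = 10, 12, 15 or 20; differences in units of the within-arm SD of the OSATS change score; two-sided 5% (one-sided 2.5%); normal data. Let δ be the true difference, video minus workshop.

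**1. What the written null allows.** Without a margin the null is δ < 0. Rejecting it requires the lower confidence limit to lie above 0, that is, a significantly better video. If δ = 0, this is the upper tail of the test: probability 0.025. Even then the finding would be superiority, not similarity.

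**2. Non-significance when the video is worse by 0.5 SD.** Noncentral t with df = 2n − 2 and noncentrality 0.5/√(2/n). For n = 10 the noncentrality is 0.5/0.447 = 1.118 on 18 df; for n = 20 it is 0.5/0.316 = 1.581 on 38 df.

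**3. Precision.** 95% CI half-width = t(0.975, 2n − 2) × √(2/n). For n = 10: 2.101 × 0.447 = 0.940 SD. For n = 20: 2.024 × 0.316 = 0.640 SD.

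**4. What a non-significant result leaves open when δ = 0.** One million simulated trials per n, keeping those with p>0.05 and counting how often the lower 95% limit falls below −0.5 or −0.8 SD.

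| n per arm | P(p>0.05), video worse by 0.5 SD | CI half-width (SD) | Lower limit < −0.5 SD | Lower limit < −0.8 SD |
|---|---|---|---|---|
| 10 | 0.815 | 0.940 | 0.832 | 0.611 |
| 12 | 0.784 | 0.847 | 0.800 | 0.537 |
| 15 | 0.738 | 0.748 | 0.751 | 0.436 |
| 20 | 0.662 | 0.640 | 0.671 | 0.296 |

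A deficit of 0.5 SD stays open in most non-significant results at every size; a deficit of 0.8 SD does so only at 10 to 12 per arm.

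**5. The adjusted regression.** With intercept, arm, baseline score and three PGY terms, df = 2n − 6, and the half-width is t(0.975, 2n − 6) × √(r × 2/n), where r is the share of variance left after adjustment.

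- r = 0.75: half-width 2.145 × √0.15 = 0.831 (n = 10) to 2.032 × √0.075 = 0.557 (n = 20). Non-significance at a 0.5 SD deficit: 0.775 to 0.574.
- r = 0.50: half-width 0.678 to 0.454. Non-significance: 0.686 to 0.416.

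**6. What a margin M could deliver.** Power to show the lower limit above −M when δ = 0, one-sided 0.025, for n = 10 to 20:

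- unadjusted: 0.184 to 0.338 for M = 0.5 SD; 0.562 to 0.869 for M = 1.0 SD;
- adjusted, r = 0.50: 0.313 to 0.584 and 0.836 to 0.991.

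By the normal approximation, n per arm for 80% power (unadjusted) is 2 × (1.960 + 0.842)²/M² = 15.7/M²: 63 for M = 0.5 SD and 16 for M = 1.0 SD.

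**The case against.** The best defense is that the stated aim is only to compare, which difference tests do, and that nothing in the SAP says p>0.05 will be called similarity. The null may be loose drafting, not a deliberate zero-margin test, so the 2.5% describes no rule the investigators adopted. The planned regression yields an estimate and standard error, so an interval can be computed and read openly. Every magnitude above rests on assumed inputs: at a 0.5 SD deficit, non-significance ranges from 82% (10 per arm, unadjusted) to 42% (20 per arm, half the variance explained), and nothing shows that 0.5 SD matters educationally. This is also a small single-program simulation study with no patient outcomes.

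Much of this stands. The aim is served by the tests, the misreading is a risk and not a stated plan, and the figures show imprecision, not measured harm. But the hypothesis and null are explicit, and they are what the trial says it will test. An interval that the plan neither commits to report nor ties to a limit gives no decision rule. If the null is loose drafting, it still needs redrafting. The modest setting bears on how simple the remedy should be, not on whether the mismatch exists.

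**Conclusion.** The concern holds, with high confidence. The primary hypothesis and the primary analysis do not match, and no outcome of the analysis as written can establish similar improvement. This follows from the text alone and does not depend on any assumed number.

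The size of the resulting risk does depend on assumptions about n, SD, alpha and the variance explained. Over 10 to 20 per arm, a non-significant result would be common even with a video half an SD worse: 66% to 82% of the time unadjusted, and still 42% to 69% if baseline score and PGY explain half the variance. This must be corrected before outcome data are seen, because a margin or reading rule chosen afterwards would not be credible. It is a fault in the hypothesis and analysis plan, not in the randomization or data collection.

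**What to change.** **Required, wording only.**

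- Replace the null with the aim of estimating the difference (video minus workshop) in OSATS change from baseline at the assessment before crossover.
- Make the already planned regression, adjusted for baseline score and PGY, the primary analysis, reported with its two-sided 95% CI. Label the t-test and Wilcoxon test as supportive.
- Add: *A p-value above 0.05 will not be reported as similarity or non-inferiority.*

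This needs no extra residents or data. The cost is giving up a formal claim of similarity.

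**Only if a claim of not worse is wanted.** Fix and justify a margin M in OSATS points before any post-intervention recording is scored. Claim non-inferiority only if the lower 95% limit lies above −M. Otherwise report the result as inconclusive or, if the upper limit is below 0, as worse. This is more than rewording: the documents give no expected gain or SD, so M needs outside data or expert judgment. With the number of residents fixed, the answer may well be inconclusive, as the power figures for M = 0.5 SD show.

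### Does the SAP need to say how the post-crossover preference score will be summarised?

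*Combined protocol and SAP*

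**What the plan says.** The Secondary outcomes list opens with "Participant preference of model between instructional video and instructional workshop". Under Protocol in detail, the rating comes at the end of the study. After the first intervention and its assessments, "those who were initially randomized to the video group will then undergo the instructional workshop"; the other group moves to the video. Only then comes the rating: "Participants will then be asked to rate their overall preference between models on a scale of 1 to 10 with 1 being the video". The top of the scale, 10, stands for the workshop. Each resident therefore gives one score on a two-ended scale, having experienced both formats.

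The Statistical Analysis Plan does not mention preference. Its general rule reads: "Categorical variables will be analyzed using chi-squared or Fisher exact tests and continuous variables will be analyzed using student t-tests". The outcomes it goes on to name are knowledge and technical skills: "The mean scores of knowledge assessment and from the Objective Structured Assessment of Technical Skills (OSATS) as well as the change in scores". The last two sentences, on linear regression and a Wilcoxon test, concern score improvement. They are the only ones that refer explicitly to the two randomized groups.

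**The concern.** The general rule gives a family of tests but no contrast. It does not say whether a 1-to-10 rating counts as categorical or continuous, whether scores are pooled over residents, or what value would mean no preference. Where the SAP does name groups, they are the randomized ones, so an analyst working by habit might run a two-sample t-test of preference by randomized group.

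That test would answer a different question. By the time of the rating, both groups have had both formats and differ only in which came first. The contrast is video-first against workshop-first. A strong preference shared by both groups would not appear in it, and an effect of order alone could be misreported as a preference. The stake is the reading of one secondary outcome.

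**Working it through.** The documents give no sample size, SD, significance level or target difference for preference, so there is no planned figure to reproduce. The check is algebra on the design and a close reading of the SAP.

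**Inputs.** The scale runs from 1 (video) to 10 (workshop), one score per resident, taken after crossover (Protocol in detail). Its arithmetic midpoint is (1 + 10)/2 = 5.5; the documents do not call this neutral. The group means below are assumed, for illustration only.

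**Step 1: what each summary estimates.** Let mV be the mean score of residents who had the video first and mW the mean of those who had the workshop first.
- Difference between randomized groups: D = mV − mW, the effect of order.
- Overall preference with equal groups: P = (mV + mW)/2.

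| mV | mW | D | P |
|---|---|---|---|
| 7.0 | 7.0 | 7.0 − 7.0 = 0 | (7.0 + 7.0)/2 = 7.0 |
| 6.5 | 4.5 | 6.5 − 4.5 = 2.0 | (6.5 + 4.5)/2 = 5.5 |

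In the first row residents lean to the workshop and D is zero. In the second they sit at the midpoint on average and D is 2 points. So D does not measure preference.

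**Step 2: does the plan call for D?** Taking the SAP sentences in turn:
- Post hoc power: silent on preference.
- General rule by variable type: no groups and no contrast stated. A one-sample t-test or confidence interval for the mean of all residents is a Student t procedure and satisfies it.
- Mean scores and changes: knowledge and OSATS only.
- Linear regression, adjusted for baseline score and training year: improvement scores only. Preference has no baseline score, so this model cannot apply to it.
- Wilcoxon test by study group and resident year: score improvement only.

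No sentence prescribes D for preference.

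**Step 3: what if an analyst tabulated preference by group anyway?** A two-group t-test is normally reported with both means, and P follows from them. In row one a reader sees 7.0 and 7.0 and knows which way residents lean. If the score were treated as categorical, the table totals would give its distribution over all residents. Unequal groups change little: with an assumed 11 and 9 residents in row two, the pooled mean is (11 × 6.5 + 9 × 4.5)/20 = 112/20 = 5.6, against 5.5 with equal groups. Only a bare difference or p-value, reported without means, would mislead.

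**The case for a change.** The best case for a change is that a SAP exists to settle such choices before data are seen, and this one is open. The general rule also has to serve ease of use, satisfaction and realism: "Residents will also be asked to evaluate model realism, ease of use, and satisfaction using a Likert scale". Those ratings are placed after the first intervention, when each resident has had one format, so a comparison of randomized groups could be right for them. An analyst applying one rule throughout would then treat preference in the same way and get the order effect. One added sentence would prevent that.

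The omission is real and the algebra is correct. The rest is weaker. The contrast with the other ratings is partly inference: the protocol does not say they are collected only once, and the model being rated may be the beef tongue model that both groups use, in which case a pooled summary would suit them too. Preference is also not a special omission. Confidence, repair time, ease of use, satisfaction, realism and the factors associated with knowledge are not named in the SAP either. Above all, the harm needs an analyst to choose a comparison the plan does not request and then report it without the group means. The wording of the question, which asks for a preference between two formats on a scale anchored by them, points to the level of the scores as the result.

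**Conclusion.** No change to the plan is needed. The SAP leaves the summary of the preference score unstated, and a comparison of the randomized groups on that score would estimate order of exposure. But the plan does not propose that comparison, its general rule permits the appropriate one-sample summary, and the instrument itself shows what to report. This is a gap that a competent analyst fills sensibly, by summarising the scores over all residents and calling any difference between sequences an order effect.

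No size can be put on a consequence, because the documents give no sample size or SD and the illustrative means are invented. The conclusion assumes only that the report shows group means or the overall distribution, as is ordinary practice. The primary OSATS comparison, the conduct of the trial and the data collected are unaffected.

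### An unspecified post hoc power analysis is the plan's only statement on cohort adequacy; the 95% confidence interval for the arm difference in OSATS change should replace it

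*Combined protocol and SAP*

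**What the plan says.** The first sentence of the Statistical Analysis Plan reads "Given the fixed set of residents, a post hoc power analysis will be performed". It does not say for which endpoint, effect size, SD, alpha or test, or how the result will be used. The cohort size is not given as a number. Under Protocol in detail, "All obstetrics and gynecology residents at the University of Alabama will be eligible for the study" and "Eligible residents who desire will be enrolled and consented for the trial", so the realised number depends on consent.

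The hypothesis, stated just before the Significance heading, begins "Our hypothesis is that participants will have similar" and goes on to improvement in technical skills. The null is that the video group does worse, and no margin is given. The primary outcome is "change in technical skills score measured as change from baseline" on the OSATS. It is compared by Student t-test and then examined further with "linear regression models, adjusting for baseline score and year of training"; a Wilcoxon test is also listed. Randomization is blocked so that "each group has a balanced number of residents in each postgraduate year training level". No confidence interval is mentioned in the text available.

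**The concern.** The sentence allows at least three different calculations.

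1. **Power at the observed effect.** This is a transform of the p-value. It is lowest when the arms are most alike, which is the result the trial hypothesises.
2. **Power at a difference chosen after the data are seen.** The answer depends on that choice.
3. **The difference detectable with a set power at the achieved number.** This is informative, but the text does not specify it. It also stays the same whatever is observed, so it does not show what the data exclude.

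If the arms come out alike, readers will ask how large a deficit with the video has been ruled out. The power analysis answers that under none of the three readings, and the plan does not commit to reporting the quantity that does. A fixed cohort explains why there is no sample-size calculation. It does not prevent a statement of expected precision.

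**Working it through.** The plan gives no figure to reproduce: no N, SD, alpha, power, effect size or margin.

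**Assumptions.** Two-sided alpha 0.05; equal arms of n = 10 to 24 residents; differences are video minus workshop, in SD units of the change score, with a higher score taken as better. No pre-post correlation is needed.

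**Step 1: observed power as a function of p.** Take t = T⁻¹(1 − p/2, 2n − 2) and d = t/√(n/2), then find the two-sided noncentral-t power at d.

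| n per arm | p = 0.05 | p = 0.20 | p = 0.50 |
|---|---|---|---|
| 10 | 0.511 | 0.243 | 0.100 |
| 15 | 0.507 | 0.245 | 0.101 |
| 20 | 0.505 | 0.246 | 0.102 |
| 24 | 0.504 | 0.247 | 0.102 |

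Each column is almost constant. Once p is known, observed power adds next to nothing, and it says nothing useful about cohort size.

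**Step 2: quantities that do respond to n.** The unadjusted 95% half-width is T⁻¹(0.975, 2n − 2) × √(2/n). At n = 15 this is 2.048 × 0.3651 = 0.748. The detectable difference at 80% power is solved from the noncentral t.

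| n per arm | Half-width (SD of change) | Detectable difference (SD of change) |
|---|---|---|
| 10 | 0.940 | 1.325 |
| 15 | 0.748 | 1.060 |
| 20 | 0.640 | 0.909 |
| 24 | 0.581 | 0.826 |

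**Step 3: the three summaries side by side at n = 15.** The interval is d ± 0.748.

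| Observed difference | p | Observed power | Detectable difference | 95% CI |
|---|---|---|---|---|
| 0 | 1.00 | 0.05 | 1.06 | -0.75 to 0.75 |
| -0.25 | 0.50 | 0.10 | 1.06 | -1.00 to 0.50 |
| -0.50 | 0.18 | 0.26 | 1.06 | -1.25 to 0.25 |

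Reading down the table, the video does progressively worse. Observed power rises, the detectable difference does not move, and only the interval shows the growing deficit that cannot be excluded.

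**Step 4: sensitivity to n.** For an observed -0.25 SD, the interval is -1.19 to 0.69 at 10 per arm (p = 0.58, observed power 0.08) and -0.83 to 0.33 at 24 per arm (p = 0.39, observed power 0.14).

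**Step 5: the adjusted interval.** If year is coded as three indicators alongside baseline score, the residual degrees of freedom are 2n − 6. The half-width is then 0.959, 0.754, 0.643 and 0.583 at n = 10, 15, 20 and 24. Chance imbalance in baseline score adds about 1 to 3% in simulation with year-balanced arms. These figures are in residual SD, a different unit from Step 2, so they must not be read as showing that adjustment widens the interval. The residual SD is normally smaller than the SD of change.

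**The case against.** The best defence is that the text never says power at the observed effect. If a detectable difference was meant, the p-value argument does not apply. The plan also attaches no decision to the power analysis, and any regression package prints a confidence interval. The expected half-width recommended here depends only on n, just as a detectable difference does, and the two could be reported together. Finally, an interval without a margin does not test the stated null.

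Some of this stands. The p-value argument is confined to the first reading. A specified detectable difference would be a legitimate planning statement, and the expected half-width is planning information of the same kind; what the interval adds after the data is its location. The missing margin is a gap that the interval alone does not close. Relying on the regression interval also gives a leading role to a model that the plan introduces only as a further examination after the t-test.

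The rest does not rescue the sentence. The plan specifies none of the three readings, and none shows which deficits the data exclude. That software prints an interval is not a commitment to report it or to judge adequacy by it.

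**Conclusion.** The concern holds. In a trial that expects similar arms, the plan commits to an undefined post hoc power analysis and does not commit to a confidence interval. Under the most damaging reading, the reported power would be about 0.05 to 0.10 at 15 per arm for observed differences of 0 to -0.25 SD, which labels the results nearest the hypothesis as the least powered. The intervals for the same results reach down to -0.75 and -1.00 SD, and that is the information a reader needs. Over 10 to 24 per arm the unadjusted half-width runs from 0.94 to 0.58 SD of change, so precision depends materially on how many residents consent.

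The cohort sizes and alpha are assumptions, and the SD of OSATS change is not in the documents, so nothing can be put in OSATS points. The logical fault depends on none of these numbers. Part of the document was removed before review and could not be checked. The trial can run as designed; this should be changed so that its most likely result is not misread.

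**What to change.** Replace the power sentence with a commitment to report the two-sided 95% confidence interval for the video-minus-workshop difference in OSATS change, from the planned regression adjusted for baseline score and year of training. Year is also the factor on which allocation is balanced. Say that adequacy and similarity will be judged from this interval, so that its standing relative to the t-test and the Wilcoxon test is clear.

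Once the number of consented residents is known, and before outcomes are scored, state the expected half-width in SD units. Do not derive a margin from what the cohort can resolve; any margin needs an educational justification. Without one, report the interval and do not infer similarity from a non-significant p-value.

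The cost is one SAP sentence. Enrolment, allocation, procedures and scoring order are unchanged. The drawbacks are that the stated precision may look unfavourable, and that SD units cannot be put on the OSATS scale until the data are in.
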